1.3 Secondary Study Endpoints

The secondary endpoint is subjective ratings of the film and side effects in order to determine whether blood levels are of significant magnitude for the participant to detect drug effects.

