7.2 Study Procedures

Part 1- Screening (Phone)

Participants will be instructed to drink water prior to their visit to help the blood draw process go smoothly. They will also be instructed that they may choose to have a meal from our cafeteria but may also bring snacks if they would like. Participants will also be informed that they can bring personal items such as laptops, books, etc. for use during their visit.

Part 1-Screening (In Person)

Participants will be re-screened for eligibility and informed consent for the appropriate part of the study will be obtained by research staff.

After consent, additional eligibility screening materials will include:

1. A review of medications and medical history
2. NIDA Drug Screener
3. Blood Pressure (systolic must be \leq 140, diastolic must be \leq 90)
4. Urine pregnancy test (if applicable)
5. Exhaled Carbon Monoxide <12 ppm

Part 1 Visit – 4 Hours

Clinical measures and questionnaires will be conducted as outlined in the table below. An IV will be inserted for access for 11 blood draws in Part 1.

Part 1: Time and Events Table						
	Screening	Part 1 Procedures				
Visit Hour	-2	-1	0	1	2	3
Administer Film			X			
Blood Draws (mins)			0-59	60-119	120-179	180-239
Baseline Blood		X				
Hour 0 Blood			Set Minutes: 5, 10, 20, 30, 40, 50 Varied by Participant: 1 minute after film dissolves			
Hour 1 Blood				Minute 60		
Hour 2 Blood					Minute 120	
Hour 3 Blood						Minute 180
Measures						
Screener 2	X					
Concomitant Meds	X					
Medical History	X					
NIDA	X					
CES-D		X				
Oropharyngeal Exam		X				X
Blood Pressure & Heart Rate	X	X	Minute 30	Minute 0, 30	Minute 0, 30	Minute 0, 30
CO Reading	X					X
Pregnancy Test	X					
Anthropometrics		X				
Demographics		X				
Nicotine Dependence		X				
Cigarette Details		X				
Tobacco Use History		X				
Minnesota Withdrawal Scale		X	Minute 15, 35, 55	Minute 20	Minute 20	Minute 20
Questionnaire of Smoking Urges		X	Minute 15, 35, 55	Minute 20	Minute 20	Minute 20
Study Product Side Effects			Minute 15, 35, 55	Minute 20	Minute 20	Minute 20
Study Product Evaluation						X
Likelihood of Use Scale						X
Payment						\$120

Film Administration, Dose and Blood Draws:

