Hour 6 Blood									Set Mins: 0,30,45					
Hour 7 Blood										Min 0				
Hour 8 Blood											Min 0			
Hour 9 Blood												Set Mins: 0, 30,45		
Hour 10 Blood													Min 0	
Hour 11 Blood														Min 0
Study Hour	-2	-1	0	1	2	3	4	5	6	7	8	9	10	11
Measures														
Screener 2	X													
Concomitant Medications	X													
Medical History	X													
NIDA	X													
CES-D	X													
Oropharyngeal Exam		X												X
Blood Pressure & Heart Rate	X	X	Min 30	Min 0, 30	Min 0, 30	Min 0, 30	Min 0, 30	Min 0, 30	Min 0, 30	Min 0, 30	Min 0, 30	Min 0, 30	Min 0, 30	Min 0
CO Reading	X													
Pregnancy Test	X													
Anthropometrics	X													
Demographics	X													
Dependence	X													
Cigarette Details	X													
Tobacco Use History		X												
Minnesota Withdrawal Scale		X	Min 50	Min 50		Min 50	Min 50		Min 50	Min 50		Min 50		Min 50

Questionnaire of Smoking Urges		X	Min 50	Min 50		Min 50	Min 50		Min 50	Min 50		Min 50	Min 50
Study Product Side Effects			Min 50	Min 50		Min 50	Min 50		Min 50	Min 50		Min 50	Min 50
Study Product Evaluation						Min 0							X
Likelihood of Use Scale						Min 0							X
Dose Awareness													X
Payment													\$240

Film Administration, Dosing and Blood draws:

Participants will receive four doses of nicotine film during this visit. Four participants each will be randomly allocated to consume four films over twelve hours in the following orders (a) 0,0,0,0mg (b) 2,2,2,2, or (c) 4,4,0,4. The first film will be administered upon completion of baseline measures (approximately 8AM). Again, participants will be instructed to allow the film to dissolve in their mouth, without chewing or swallowing it and to report to the researcher when he or she feels that the film has completely dissolved. Films will be administered every three hours (approximately 11 AM, 2 PM, and 5 PM). The Time and Events table above details the order of events and timing for biomeasures, questionnaires and 20 total blood draws.

Payment:

Participants will receive \$240 for completing this visit.

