7.4 Test Article(s) (Study Drug(s) and/or Study Device(s))

7.4.1 Description

Nicotine orally dissolving films (ODF) will be provided in doses of 0, 2, or 4 mg. The active pharmaceutical ingredient in Nicotine ODF is nicotine polacrilex (20%, USP). The film used in Nicotine ODF has a muco-adhesive property, i.e. it can adhere to the oral mucosa and allow the drug to be absorbed through oral mucosa. After placement in the oral cavity, nicotine ODF dissolves over a 5-10 minute period. The unit-dose dosage is in the form of a 1 in x 1 in square and weighs about 100 mg. Nicotine films are not available in the United States in a non-investigational setting. See table below for composition information.

Nicotine Oral Film Formulations: 0, 2, and 4 mg

Nicotine ODF Dosage		Placebo, 0 mg	2 mg	4 mg
Material Name	Grade	Weight, g		
Sodium Bicarbonate	USP/EP	1.97	1.71	1.64
Propylene Glycol	USP/EP	23.66	20.55	19.68
Nicotine Polacrilex 20%	USP	0.00	17.81	37.72
Purified Water	USP	209.04	205.45	196.80
Ethanol anhydrous	USP	110.44	119.85	114.80

Polyox N10 (Polyethylene oxide)	NF	134.10	116.42	111.52
Saccharin	Food Grade	2.45	2.12	2.03
Cocoa Powder	Food Grade	1.77	1.71	1.97
L-Menthol	USP	9.98	8.66	8.30
Peppermint oil	USP	6.19	5.38	5.15
Methylparaben	NF	0.20	0.17	0.20
Propylparaben	NF	0.20	0.17	0.20
Total		500.00	500.00	500.00

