11.6 Frequency of review of cumulative data

All the data from the first part of the study (including the results of the blood nicotine analyses) will be reviewed by the leadership group, including [name], before initiation of the next part. If necessary, the doses planned for the next part or the timing of the blood samples may be adjusted accordingly and a modification of study protocol submitted to the IRB.

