- **Nicotine film side effects:** Excess nicotine can cause mild symptoms such as nausea, dizziness, diarrhea and rapid heartbeat. Occasionally these symptoms are more severe (e.g. vomiting) such as when an individual receives more nicotine than they are accustomed to. This, however, is unlikely to occur with the doses used in this study. Additional side effects of the film may include hiccups.

- **Possible effects on the oral cavity.** In order to assess local toxicity of the study product, the CRC nurse assisting with the clinic visit will perform an oropharyngeal exam at the beginning of the visit prior to the participant receiving the study product as well as at the end of the visit after study product use is complete. Any changes will be assessed and documented. During the visit, after each film administration, participants will be asked to report side effects including any mouth discomfort or irritation via a questionnaire. If indicated, participant would discontinue study product use. Lesions of the oral mucosa are not anticipated as daily dissolution of several 2 mg sublingual nicotine tables (range 1-12/day over a 6 month period) led to only mild and transient effects on the oral mucosa[24]
- **Incidental Finding:** None of the tests carried out in this study are intended to provide diagnoses for clinical purposes, but participants will be alerted to findings that should be discussed with a healthcare provider (such as high blood pressure)

The participant may be removed from the research study without his or her permission because the participant does not follow the instructions for the study, has an adverse reaction to the study product (irregular heartbeat, palpitations, tachycardia (resting heart rate persistently greater than 100 beats per minute), has symptoms of nicotine overdose such as nausea, vomiting, dizziness, weakness, or rapid heartbeat, or has symptoms of an allergic reaction.

Participants are instructed to please call the Principal Investigator, [name] [name]., at [contact] during business hours or [contact] after business hours if they:

- Experience any symptoms after the study is completed that they believe may be related to participation in the study
- Have questions, complaints, or concerns about the research

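### In Part 2, the only part with repeated films, the side-effects form is first given 50 minutes after each film, so early effects rest on recall or unprompted report and the 30-minute blood draw has no paired rating

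*Combined protocol and SAP*

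**What the plan says.** Section 1.3: "The secondary endpoint is subjective ratings of the film and side effects". The section gives the purpose as finding out whether blood levels are large enough for participants to notice drug effects.

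Section 7.2, Part 1 table: one film is given, and the side-effects row in Hour 0 reads "Minute 15, 35, 55". It is then marked at minute 20 of Hours 1, 2 and 3.

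Section 7.2, Part 2 table: films are given at Hours 0, 3, 6 and 9. The "Study Product Side Effects" row is marked at Min 50 of each of those hours and at Min 50 of a following hour, and at no earlier minute after any film.

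Section 7.4.1: "nicotine ODF dissolves over a 5-10 minute period".

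Section 12.0, on effects in the mouth: "During the visit, after each film administration, participants will be asked to report side effects including any mouth discomfort or irritation via a questionnaire". No minute is given. The oropharyngeal exam is scheduled only before the first film and at the end of the visit.

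**The concern.** Part 2 is the only source of data on repeated films, and it asks about side effects later after each film than Part 1 does. Two things are at stake.

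- **The secondary endpoint.** Relating what participants feel to their nicotine level works best when ratings sit close to blood samples. Part 1 is built that way. In Part 2 the 30-minute draw, the first after each film, has no rating near it.
- **Oral tolerability.** Between the two oropharyngeal exams, this form is the only scheduled check for mouth irritation. When it is first given, the film has been gone for most of an hour. A brief effect has to be remembered or volunteered to be recorded.

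**Working it through.** No sample size or power figure is involved; the check is a mapping of times.

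**Inputs**
- Part 2 films: Hours 0, 3, 6, 9, which is 0, 180, 360 and 540 minutes (7.2). Minute 0 of the film hour is taken as the time of administration.
- Part 2 side-effect forms: Min 50 of Hours 0, 1, 3, 4, 6, 7, 9 and 10 as the table reads in the text available, which is 50, 110, 230, 290, 410, 470, 590 and 650 minutes. The last mark may be shifted by a column, since the withdrawal-scale row ends at Hour 11. This does not affect the first form after any film.
- Part 1 side-effect forms: 15, 35, 55, 80, 140 and 200 minutes.
- Dissolution: 5-10 minutes (7.4.1).

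**Check that the tables are read correctly.** Counting draws gives 11 in Part 1 (baseline; six set times plus one after dissolution; minutes 60, 120 and 180). Part 2 gives 1 + 4 + 3 × 5 = 20. Both match the totals in 7.2.

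**Time from film to form, Part 2.** Form time minus film time gives 50 and 110 minutes for each of the four films (for example 230 − 180 = 50 and 290 − 180 = 110).

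**Time from dissolution to first form**
- Part 1: 15 − 10 = 5 to 15 − 5 = 10 minutes.
- Part 2: 50 − 10 = 40 to 50 − 5 = 45 minutes.
- Part 2 asks 50 − 15 = 35 minutes later than Part 1, with one form in the first hour after a film against three.

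**Pairing with blood draws**

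| | Draw (min) | Next form (min) | Gap (min) |
|---|---|---|---|
| Part 1 | 10 | 15 | 5 |
| Part 1 | 30 | 35 | 5 |
| Part 1 | 50 | 55 | 5 |
| Part 2 | 30 | 50 | 20, with the 45-minute draw in between |
| Part 2 | 45 | 50 | 5 |

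**Films affected.** 12 participants × 4 films = 48. Placebo films: 4 × 4 = 16 in the all-0 mg arm, plus 4 × 1 = 4 in the 4,4,0,4 arm, so 20. Films containing nicotine: 48 − 20 = 28. Irritation from the film itself could follow any of the 48; nicotine effects only the 28.

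**What the recall period would change.** The documents do not state it, so both cases are assumptions.
- If the form asks about the present moment, an effect that has resolved by minute 50 is not scored.
- If it asks about the time since the last form, the minute-50 form after films 2, 3 and 4 covers (180 − 110) + 50 = 120 minutes: 70 belonging to the previous film and 50 to the new one. Early effects are then included, but recalled late and mixed with the earlier film's tail.
- If it asks about the time since the latest film, the early window is covered, subject to recall over 50 minutes.

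**The case against.** The case for leaving the table alone is substantial.

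- **Part 2 is internally matched.** All three arms, including placebo, are asked at the same minutes, and each film is first rated at minute 50. This stands: the late form does not bias comparisons between arms.
- **No comparison between the parts is planned.** A reader might infer that repeated dosing will look better tolerated than a single film merely because the question comes later. Sections 9.2 and 11.7 state only change from baseline, so the documents do not support that as a flaw in a planned analysis. It would arise only if someone set the two parts side by side descriptively.
- **Early effects need not be missed.** Participants remain on site (7.4.4) and are supervised with symptoms recorded (12.0). They tell the researcher when each film has dissolved, and have blood pressure and heart rate taken at minute 30. This stands as mitigation. But these are unprompted reports and vital signs, not the endpoint questionnaire.
- **Under-scoring is not shown.** Nothing in the documents says symptoms peak during or soon after dissolution. This stands.
- **A form precedes every new film.** Forms at 50 and 110 minutes both fall before the next film at 180, and section 12.0 promises no particular minute. So there is no contradiction with 12.0, and no film follows another without a prompted question.
- **Minute 50 lies between the 45- and 60-minute draws,** which serves the endpoint in part. The 30-minute draw remains unpaired.

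A reader might also take section 11.6 to freeze the questionnaire times, since it says "the doses planned for the next part or the timing of the blood samples may be adjusted accordingly" and does not mention them. That is not supported: sections 7.4.2 and 11.5 already allow the protocol to be adjusted, so 11.6 needs no edit for this purpose.

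**Conclusion.** The timing gap is real and holds for every Part 2 film: first form at 50 minutes, 40-45 minutes after stated dissolution, against 15 minutes (5-10 after dissolution) in Part 1. The 30-minute draw has no paired rating. The supported consequence is limited: short-lived effects after repeated films may be recalled late or depend on volunteered reports, and the link between early blood levels and felt effects is weaker than in Part 1.

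A reader might conclude that side effects will be under-scored or missed. The documents do not establish this. Without the recall period and the symptom time course, no size can be put on the loss. This is a low-cost improvement to a secondary endpoint and to oral-tolerability monitoring; it is not an error that invalidates an analysis. It rests on minute 0 being the time of administration and on the stated 5-10 minute dissolution.

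**What to change.** In the Part 2 Time and Events Table, add the side-effects form at Min 15 and Min 35 of Hours 0, 3, 6 and 9. These are Part 1's own times. Min 35 falls 5 minutes after the 30-minute draw, and neither time coincides with the draws at 30 and 45 or the vital signs at 30. Min 15 still comes after dissolution, as it does in Part 1.

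Keep all existing Min 50 forms, including those in the second hour, which are the last scheduled questions before the next film.

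The cost is 2 × 4 = 8 more short self-report forms per participant, doubling the present eight to sixteen, or 12 × 8 = 96 across Part 2. No new instrument is needed, and participants are already supervised for the 12-hour visit. If burden is a concern, add only one early time: Min 35 serves the pairing with blood levels, and Min 15 serves prompt capture of mouth irritation.

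If tolerability is described across the two parts, do so only at near-matched minutes (15, 35, and 50 against 55). With the table unchanged, the only such match in the first hour is 50 against 55.

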7.3 Duration of Participation

Duration of participation is dependent on which part of the study the participant is enrolled in. The study visit for Part 1 will last approximately four hours. The study visit for Part 2 will last approximately twelve hours.

7.4 Test Article(s) (Study Drug(s) and/or Study Device(s))

7.4.1 Description

Nicotine orally dissolving films (ODF) will be provided in doses of 0, 2, or 4 mg. The active pharmaceutical ingredient in Nicotine ODF is nicotine polacrilex (20%, USP). The film used in Nicotine ODF has a muco-adhesive property, i.e. it can adhere to the oral mucosa and allow the drug to be absorbed through oral mucosa. After placement in the oral cavity, nicotine ODF dissolves over a 5-10 minute period. The unit-dose dosage is in the form of a 1 in x 1 in square and weighs about 100 mg. Nicotine films are not available in the United States in a non-investigational setting. See table below for composition information.

Nicotine Oral Film Formulations: 0, 2, and 4 mg

Nicotine ODF Dosage		Placebo, 0 mg	2 mg	4 mg
Material Name	Grade	Weight, g		
Sodium Bicarbonate	USP/EP	1.97	1.71	1.64
Propylene Glycol	USP/EP	23.66	20.55	19.68
Nicotine Polacrilex 20%	USP	0.00	17.81	37.72
Purified Water	USP	209.04	205.45	196.80
Ethanol anhydrous	USP	110.44	119.85	114.80

Polyox N10 (Polyethylene oxide)	NF	134.10	116.42	111.52
Saccharin	Food Grade	2.45	2.12	2.03
Cocoa Powder	Food Grade	1.77	1.71	1.97
L-Menthol	USP	9.98	8.66	8.30
Peppermint oil	USP	6.19	5.38	5.15
Methylparaben	NF	0.20	0.17	0.20
Propylparaben	NF	0.20	0.17	0.20
Total		500.00	500.00	500.00

7.4.2 Treatment Regimen

Nicotine films will be administered orally. They are used by placing a film on the tongue, closing the mouth and pressing the tongue gently to the roof of the mouth. The film will dissolve in the mouth within 5-10 minutes. Three doses of nicotine film will be used in this study: 0, 2, and 4 mg. During the first part, participants will receive one dose of either 0, 2, or 4 mg film. After the first part is complete, reactions to dosing will be evaluated and adjustments will be made if necessary before proceeding to the second part. Should adjustments need to be made, modified protocol and consent documents will be submitted to the IRB prior to proceeding to Part 2. During the second part, participants will receive four doses of nicotine film at three hour intervals over the course of twelve hours. There will be three dosing groups and four participants each will receive all 0 mg films, all 2 mg films, or a sequence of 4,4,0,4 mg films.

7.4.3 Method for Assigning Subject to Treatment Groups

Participants will be randomized to one of three dosing groups based on a pre-determined random number sequence generated by the study statistician, [name] [name].

7.4.4 Subject Compliance Monitoring

Subjects will remain on-site for the duration of each visit and will be given the study product by the researcher who will monitor that the dose was taken as directed.

7.4.5 Blinding of the Test Article

Blinded packages of the test article will be created for each participant prior to their arrival by an unblinded study staff member. Both the participant and the researcher administering the film will be blinded to the dose of the test article.

7.4.6 Receiving, Storage, Dispensing and Return

7.4.6.1 Receipt of Test Article

The test article will be manufactured by Bionex Pharmaceuticals LLC in its North Brunswick, NJ, facility under cGMP conditions, and shipped directly from Bionex to Penn State Hershey. The packaged test article has been tested to be stable at temperatures up to 30°C for 12 months, and therefore will be shipped via courier under room temperature.

Each film (test article) will be individually contained in a sealed, chemical- and moisture-resistant multi-component (polyester/aluminized) laminated pouch. Number of pouches, cartons, and labeling information, will be made according to the Clinical Trial Protocol.

7.4.6.2 Storage

The nicotine films will be stored in the Investigational Drug Pharmacy at Hershey Medical Center in accordance with guidelines provided by the manufacturer.

7.4.6.3 Preparation and Dispensing

The test article will be randomized by an unblinded study team member according to the randomization code created by the study statistician. The study treatment will be administered by blinded study staff who will provide each dose of the study product to the blinded researcher.

7.4.6.4 Return or Destruction of the Test Article

Any remaining study product will be destroyed at the end of the study.

7.4.6.5 Prior and Concomitant Therapy

A medical history and evaluation of all concomitant medications will be reviewed prior to participant starting the study. Participants currently using FDA approved cessation medications will be excluded.

8.0 Data and Specimen Banking For Future Undetermined Research

After the blood is analyzed, it will be destroyed.

8.1 Data and/or specimens being stored

N/A

8.2 Location of storage

N/A

8.3 Duration of storage

N/A

8.4 Access to data and/or specimens

N/A

8.5 Procedures to release data or specimens

N/A

8.6 Process for returning results

N/A

9.0 Statistical Plan

9.1 Sample size determination

Initial testing by [name] (a principal investigator on the project and co-inventor of the oral nicotine film) has demonstrated that the plasma nicotine levels produced by oral nicotine film are comparable in size to those produced by consumption of a similar dose of Nicorette gum. Pharmacokinetic studies have shown that Nicorette gum has robust effects on plasma nicotine concentration that are readily detectable in sample sizes that are approximately the same as (e.g., Benowitz, Jacob, & Savanapridi, 1987; Lunell & Lunell, 2005), or smaller than (e.g., Shiffman et al., 2009), the one proposed here (n=12). Based upon such work, we are confident that we will have sufficient power to achieve the aim of the proposed research.

9.2 Statistical methods

Paired sample t-test (or nonparametric Wilcoxon Rank-Sum test) will be used to examine the changes in the outcome measures (plasma nicotine, subjective measures, HR, BP) from the baseline.

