7.0 Study Design and Procedures

7.1 Study Design

This will be a randomized, double blind, parallel group pharmacokinetics study that will occur in two parts. The researchers and participants will be blind to the dosing of the nicotine films. Participants may participate in one or both parts of the study.

Part I: Participants are randomized to receive one dose of 0, 2, or 4 mg nicotine films

Part II: Participants are randomized to receive one dose every three hours for a total of four doses of either all 0 mg, all 2 mg or 4,4,0,4 mg nicotine films.

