Participants will receive one film at this visit after completing baseline measures (approximately 8 AM). They will be instructed to allow the film to dissolve in their mouth without chewing or swallowing it and to report to the researcher when he or she feels that the film has completely dissolved. Four participants each will receive a randomly allocated dose of either (a) 0mg, (b) 2mg or (c) 4mg oral nicotine film. The Time and Events table above details the order of events and timing for biomeasures, questionnaires and 11 total blood draws. However, if the film dissolves within one minute of a set blood draw time, the blood draw that is to be completed one minute after the film dissolves will be omitted.

Payment:

Participants will receive \$120 for completing this visit.

Part 2- Screening (Phone)

Participants will be instructed to drink water prior to their visit to help the blood draw process go smoothly. They will also be instructed that they may choose to have meals from our cafeteria but may also bring snacks if they would like. Participants will also be informed that they can bring personal items such as laptops, books, etc. for use during their visit.

Part 2- Screening (In Person)

Participants will be re-screened for eligibility and informed consent for the appropriate part of the study will be obtained by research staff.

After consent, additional eligibility screening materials will include:

1. A review of medications and medical history
2. NIDA Drug Screener
3. Blood Pressure (systolic must be \leq 140 mm Hg, diastolic must be \leq 90 mm Hg)
4. Urine pregnancy test (if applicable)
5. Exhaled Carbon Monoxide <12 ppm

Part 2 Visit- 12 hours

Clinical measures and questionnaires will be conducted as outlined in the table below.

An IV will be inserted for access for 20 blood draws in Part 2. Time and contents of participant meals/snacks will also be recorded so as to enable researchers to assess food intake and timing as it relates to timing of nicotine absorption from the film.

Part 2: Time and Events Table														
	Screening		Part 2 Procedures											
Study Hour	-2	-1	0	1	2	3	4	5	6	7	8	9	10	11
Administer Film			X			X			X			X		
Blood Draws														
Baseline Blood		X												
Hour 0 Blood			Min 30, 45											
Hour 1 Blood				Min 0										
Hour 2 Blood					Min 0									
Hour 3 Blood						Set Mins: 0, 30, 45								
Hour 4 Blood							Min 0							
Hour 5 Blood								Min 0						

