11.7 Statistical tests

Statistical methods will be used to analyze the safety data to determine whether harms are occurring. Paired sample t-test (or nonparametric Wilcoxon Rank-Sum test) will be used to examine the changes in the outcome measures (plasma nicotine, subjective measures, HR, BP) from the baseline.

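### Sections 9.2 and 11.7 name the rank-sum test, which is for independent samples, as the alternative to the paired t-test; the paired counterpart is signed-rank, to be named with the analysis unit

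*Combined protocol and SAP*

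**What the plan says.** Section 9.2 of the combined protocol and SAP consists of one sentence: "Paired sample t-test (or nonparametric Wilcoxon Rank-Sum test) will be used to examine the changes in the outcome measures", listing plasma nicotine, subjective measures, heart rate and blood pressure, with change taken from baseline. Section 11.7 opens with "Statistical methods will be used to analyze the safety data to determine whether harms are occurring" and then repeats that sentence. The signed-rank test is not named anywhere.

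Section 7.1 describes the design: "This will be a randomized, double blind, parallel group pharmacokinetics study that will occur in two parts". Section 7.2 sets the group sizes. For Part 1: "Four participants each will receive a randomly allocated dose of either (a) 0mg, (b) 2mg or (c) 4mg oral nicotine film". For Part 2: "Four participants each will be randomly allocated to consume four films over twelve hours". Section 7.4.2 repeats four per group for Part 2, and section 9.1 gives the sample size as 12. Neither 9.2 nor 11.7 describes a comparison between dose groups, or says whether the change from baseline is tested within a dose group, in the pooled active groups or in everyone in a part.

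**The concern.** A change from baseline is a within-person quantity. The paired t-test uses it as such. The rank-sum test does not: it compares the set of baseline values with the set of post-dose values as if they came from different people. Differences between people then stay in the noise.

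Two things are at stake. If the data look non-normal and the analyst follows the plan literally, the nonparametric result will usually be too conservative, and modest changes can be missed. Heart rate, blood pressure and subjective ratings are more exposed to this than a large rise in plasma nicotine. The same sentence also governs the safety data in 11.7, where missing a modest change is the less welcome error.

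**Working it through.** **Inputs from the documents.** Four per dose group and three groups per part (7.2, 7.4.2), so 3 × 4 = 12, which agrees with 9.1. Two active groups per part give 2 × 4 = 8. The plan states no power figure, alpha, sidedness, SD, correlation or expected shift, so there is no power calculation to reproduce.

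**Assumptions.** Two-sided 0.05; normal data; correlation ρ between a person's baseline and post-dose values from 0 to 0.8; shifts in units of the baseline SD; equal SDs unless stated.

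**Why pairing matters.** With equal SDs σ, the SD of the change is σ√(2(1 − ρ)). At ρ = 0.5 this is σ√1 = 1.00σ; at ρ = 0.8 it is σ√0.4 = 0.63σ. A 0.6 SD shift is therefore 0.60 and 0.95 SDs of change respectively. Signed-rank gains from that reduction; rank-sum does not.

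**Power by simulation**, with exact null distributions for both rank tests, rank-sum v signed-rank:

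| n, shift | ρ = 0 | 0.2 | 0.5 | 0.8 |
|---|---|---|---|---|
| 12, 0.6 SD | 26 v 24% | 24 v 29% | 21 v 43% | 16 v 81% |
| 8, 0.6 SD | 19 v 15% | 17 v 18% | 14 v 26% | 10 v 57% |
| 12, 1 SD | 61 v 56% | 62 v 66% | 64 v 85% | 71 v >99% |
| 8, 1 SD | 44 v 35% | 44 v 42% | 44 v 61% | 46 v 94% |

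For a 2 SD shift, rank-sum power is 95 to 99% at n = 8 and at least 99% at n = 12, so little can be lost.

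**Type I error of rank-sum, n = 12, equal SDs.** 4.5%, 2.8%, about 0.8% and about 0.05% at ρ = 0, 0.2, 0.5 and 0.8.

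**Unequal spread.** With equal means but a post-dose SD four times the baseline SD (assumed), rank-sum type I error at ρ = 0 and 0.2 is 7.1% and 6.1% at n = 8, and 7.0% and 5.9% at n = 12. At ρ = 0.5 it is just under 5%.

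**What signed-rank can attain.** The smallest two-sided exact p is 2/2ⁿ: 2/16 = 0.125 at n = 4; 2/256 = 0.0078 at n = 8; 2/4096 = 0.0005 at n = 12. In one dose group it can never reach 0.05.

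**The alternative at n = 4.** Rank-sum v paired t for a 0.6 SD shift: 7 v 9%, 5 v 11%, 4 v 14% and 3 v 27% across the four correlations. For 2 SD: 49 v 49%, 49 v 57%, 50 v 76% and 51 v 98%. The 95% confidence interval half-width for the mean change is t(0.975, n − 1)/√n SDs of change: 1.59 at n = 4, 0.84 at n = 8 and 0.64 at n = 12.

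**The case against.** The strongest reply is that little turns on this. The first-named test is right, and no decision in the plan is tied to a p-value: section 11.6 sends all Part 1 data to the leadership group before Part 2, and section 11.5 provides for immediate review of individual serious events. If the film raises plasma nicotine strongly, either test will show it at n = 8 or 12. This stands, and it limits the weight of the point. It does not make the named test correct.

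A second reply is that rank-sum was meant for comparing doses, since the design is parallel-group. The sentence does not support that: it offers rank-sum as the substitute for a paired test of change from baseline.

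A third is that in a group of 4, the only size the protocol assigns, signed-rank cannot reach 0.05 while rank-sum can. That is true, and it is why the unit belongs with the rename. It does not justify rank-sum, because the paired t-test has equal or greater power in the n = 4 cases shown.

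A reader might infer three stronger things. One is that rank-sum can only be conservative here; the unequal-spread result shows otherwise. Another is that renaming achieves nothing without further specification; at n = 8 or 12 it is sufficient. A third is that 11.7 would take a non-significant test as proof of no harm; the documents do not say so, and individual safety review is planned separately.

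**Conclusion.** The point holds as an error in the named alternative, in two sections. It is not an error in the first-named analysis, and it may be no more than a wrong word.

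Its effect runs from negligible to large. At zero correlation rank-sum is slightly the more powerful test; at correlation 0.5 to 0.8 with modest shifts it gives up half or more of the signed-rank power in the 0.6 SD cases at n = 12. Under equal SDs and positive correlation it is conservative. With a much larger post-dose spread and low correlation it can be mildly anti-conservative, at about 6 to 7%. All of these figures rest on assumed normality, SDs, correlation, shift and alpha.

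The unstated unit is an omission rather than an error, but it decides whether the corrected test can ever be significant. Alpha, sidedness and the rule for choosing the alternative are likewise missing detail, and this point does not depend on them.

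**What to change.** In 9.2 and 11.7, replace the rank-sum test with the exact Wilcoxon signed-rank test, and state the analysis unit alongside it.

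- If the unit is the dose group of 4, rely on the paired t-test with confidence intervals and label signed-rank descriptive.
- If the active groups are pooled (8), say that this mixes doses. If all 12 are pooled, say that 4 placebo participants are included.
- If a comparison between doses is wanted, name rank-sum on change scores separately for it. With 4 against 4 its smallest two-sided p is 2/C(8,4) = 2/70 = 0.029.

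The cost is a test name in two places and a sentence on the unit, with no change to data collection. The downside is that with 4 per group the paired t-test rests on a normality assumption that four values cannot check, and its 95% interval is wide, at ±1.59 SDs of change.
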